6.2 Inclusion Criteria

Deviations from inclusion criteria are not allowed because they can potentially jeopardize the scientific integrity of the study, regulatory acceptability or participant safety. Therefore, adherence to the criteria as specified in the protocol is essential.

Participants eligible for enrollment in the study must meet all the following criteria:

- Male and female subjects ≥18 years of age
- In good general health as determined by a thorough medical history and physical examination, and vital signs
- Clinical diagnosis of mild to moderate atopic dermatitis according to the criteria of Hanifin and Rajka
- Mild to moderate Atopic Dermatitis area and severity index [EASI] 10-21
- A score of at least ≥ 5 points (moderate pruritus) on the VAS for pruritus
- A minimum of 10% and not more than 30% of the subjects' BSA affected by atopic dermatitis (affected is defined by physical examination findings: erythema, edema, scaling, lichenification, excoriation, with the excoriation serving as the physical examination correlate of pruritus)
- An IGA score of 2-3
- Patient has a history of AD for ≥ 12 months
- The ability to understand and sign a written informed consent form, which must be obtained prior to treatment

6.3 Exclusion Criteria

Deviations from exclusion criteria are not allowed because they can potentially jeopardize the scientific integrity of the study, regulatory acceptability or participant safety. Therefore, adherence to the criteria as specified in the protocol is essential.

Participants will be excluded from the study if any of the following criteria are met:

- Pregnant and lactating women by urine pregnancy testing
- Subjects with any significant clinical abnormalities which may interfere with study participation
- Any skin condition which may interfere with evaluation of AD
- Atopic dermatitis only on the head or scalp
- Subjects with Atopic dermatitis on the face
- Unstable or actively infected atopic dermatitis
- Patients suffering from pruritus from conditions other than AD
- Patients with chronic pruritus due to systemic disease
- Patients with conditions requiring inhaled steroids

- Have concurrent skin disease of such severity in the study area that it could interfere with the study evaluation
- Have active skin infections on the treatment area
- Have received or planning to receive topical corticosteroids, topical coal tar, topical sulfur, topical PDE-4 inhibitors, topical antihistamines, topical antiseptics or antibiotics, topical antifungals, bleach baths, UVA or UVB phototherapy, oral/IV/inhaled steroids, antibiotics/antiviral/antifungal agents, oral probiotics, glucocorticoids treatment, calcineurin inhibitors, immunomodulating biologic agents, systemic glucocorticoids, systemic immunosuppressive or immunomodulatory agents within 2 weeks of Baseline visit.
- Current or recent history (≤ 3 months of systemic use of OtrexupTM, Rasuvo®, Rheumatrex® and TrexallTM or its generic versions such as Methotrexate
- History of being seropositive for human immunodeficiency virus (HIV) at screening by laboratory testing at Screening
- History of being positive for Hepatitis B virus surface antigen (HBsAg) or positive Hepatitis C virus antibody (HCV Ab) at screening by laboratory testing at Screening
- History of renal disease
- Use of any investigational drugs within the previous 30 days prior to dosing or within a period of less than five times the drug's half-life, whichever is longer
- Use of any biologic within a period of 5 times its half-life
- Use of vinegar or bleach baths within 2 weeks of starting the study

7 PARTICIPANT ENROLMENT

7.1 Consenting Participants

Informed consent for participation in the study must be obtained before performing any study-specific procedures.

Informed Consent Forms for enrolled participants and for participants who are not subsequently enrolled will be maintained at the study site in secure study files. Consent will be obtained by trained research study staff trained in taking informed consent. The study will be explained with the opportunity for the participant to ask questions. If a participant wishes to enter the study, a consent form will be completed and signed.

7.2 Screening for Eligibility

After informed consent has been obtained, to determine participant eligibility for enrollment in the study, screening assessments will be performed within 1 week (-21 to -14 days) prior to starting the Washout period (-14 to -1). All screening evaluations must be completed and reviewed to confirm that participants meet all eligibility criteria before Washout period and subsequent randomization on Day 1. Subjects will be asked to undergo a 2 week (-14 to -1) washout period prior to the Baseline procedure. During the washout period, subjects will be asked to stop taking bleach or vinegar baths and start using cleanser and moisturizer provided by the sponsor on as needed bases.

At least 30 days of the participant's medical history and medication use will be requested from their PCP or treating physicians and reviewed by the study staff. A complete physical examination including height, weight and vital signs will be performed.

All screening assessments are listed in the Time and Events Table (Appendix A). A participant must meet all inclusion criteria, and none of the exclusion criteria, to be enrolled and randomized in this study. The Investigator and team will maintain a screening log to record details of all persons screened and to confirm eligibility or record reasons for screening failure, as applicable.

7.3 Study Withdrawal and Withdrawal From Investigational Product and Stopping Criteria

A participant may withdraw from the study at any time at his/her own request, or may be withdrawn at any time at the discretion of the Investigator.

Reasons for withdrawal (participants who refuse to complete any remaining study visits) or discontinuation (participants who prematurely stop the application) at any time during the study may include, but are not limited, to the following:

- For safety reasons, either at the discretion of the Investigator or at the participant's request
- For protocol violations at the discretion of AOBiome
- Due to concomitant therapy that could interfere with the results of the study (the Investigator will report all such information on the CRFs and decide, in accordance with AOBiome, whether the participant is to be withdrawn).

The reason for participant study withdrawal will be recorded in the electronic Case Report Form (eCRF). Data from participants withdrawing from the study will be considered evaluable up to the point at which they are withdrawn using the same criteria for evaluability as for participants who complete the study.

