15.4.6 Handling of dropouts or missing data

Missing data will not be imputed for analysis. Subjects who dropout after enrollment but prior to randomization will be replaced.

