### 2. SUBJECT POPULATION

### 2.1. Population Definitions

The following subject populations will be evaluated and used for presentation and analysis of the data:

- x Intent-to-Treat (ITT) Population: Includes all randomized subjects. Subjects will be analyzed according to the treatment assigned by the randomization schedule. The ITT population will be the primary population for efficacy analyses.
- x Safety Population: Includes all subjects who received at least 1 dose of study medication. Subjects will be analyzed according to the study drug received.
- Per Protocol (PP) Population: Includes subjects who administered at least 50% of IP, have at least one baseline and post baseline Day 28 visit and did not have any major protocol violations. The PP population will be used for supportive summaries of efficacy data.

The ITT population is the primary population for the analysis of efficacy parameters. A subset of efficacy parameters will be evaluated for the PP population (see Section 4.3). The Safety population is the primary population for the analysis of safety endpoints.

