### 2.2. Protocol Deviations

Deviations will be summarized on the ITT patient population and may include:

- x Inclusion or exclusion criteria not satisfied.
- x Deviations related to the Investigational Product administration
- Not permitted concomitant medications.

At the discretion of the Sponsor, major protocol deviations, as determined by a review of the data prior to unblinding of the study results and the conduct of statistical analyses, may result in the removal of a subject's data from the PP population. The Sponsor or designee will be responsible for producing the final protocol deviation file (formatted as a Microsoft Excel file), in collaboration with Veristat and the data monitoring group as applicable. This file will include a description of the protocol deviation and clearly identify whether or not this violation warrants exclusion from the PP population. The file will also classify the deviations as major vs minor deviations. This file will be finalized prior to hard database lock.

All protocol deviations will be presented in a data listing.

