### 3.10. Missing, Unused, and Spurious Data

In general, there will be no substitutions made to accommodate missing data points. All data recorded on the case report form will be included in data listings that will accompany the clinical study report.

When tabulating adverse event data, partial dates will be handled as follows. If the day of the month is missing, the onset day will be set to the first day of the month unless it is the same month and year as study treatment. In this case, in order to conservatively report the event as treatment-emergent, the onset date will be assumed to be the date of treatment. If the onset day and month are both missing, the day and month will be assumed to be January 1, unless the event occurred in the same year as the study treatment. In this case, the event onset will be coded to the day of treatment in order to conservatively report the event as treatment-emergent. A missing onset date will be coded as the day of treatment.

In all cases, the resulting date will be compared to the AE end date, if present. If the imputed start date is later than the AE end date, then the start date will be set equal to the end date. The imputed start date is used only for determining treatment emergence; data listings will present the partial date as recorded on the CRF.

Missing AE severities will not be imputed and will be considered missing in any tabulations of AE severity. When relation of AEs to the study drug is missing, the AE will be considered "related" to study drug.

22

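### Subjects whom the sponsor withdraws from the study for protocol violations lose their later ITT data, although the PP set already exists to handle violations

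*Protocol*

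**What the plan says.** Protocol 7.3 lists, as a possible reason for withdrawal or discontinuation, "For protocol violations at the discretion of AOBiome". Protocol 13.4 and SAP 1.2.2 repeat it. None of the three states which violations qualify, how serious they must be, or who adjudicates. The list covers two different events, leaving the study and stopping application, and does not say which one a violation leads to.

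Data from a withdrawn subject "will be considered evaluable up to the point at which they are withdrawn" (Protocol 7.3). On missing values, Protocol 15.4.6 says "Missing data will not be imputed for analysis" and SAP 3.10 says "In general, there will be no substitutions made to accommodate missing data points".

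SAP 2.1 defines ITT thus: "Includes all randomized subjects. Subjects will be analyzed according to the treatment assigned by the randomization schedule". It adds: "The ITT population will be the primary population for efficacy analyses". The PP set is limited to subjects who, among other conditions, "did not have any major protocol violations". SAP 2.2 sets out how that is decided. The sponsor reviews deviations before unblinding, and major ones "may result in the removal of a subject's data from the PP population". The deviation file is finalized before database lock.

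**The concern.** ITT is the primary efficacy population because it keeps the groups as randomized. A discretionary exit after randomization works against that when the subject's later outcomes are then lost. The PP set has a documented route for violators, with a review before unblinding that affects PP only. The withdrawal clause adds a second route, used while the trial is running and without stated criteria, and its effect reaches the ITT results.

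Violations need not be independent of outcome. The deviation types named in Protocol 15.5 and SAP 2.2 include problems with product administration and non-permitted medication. Either can follow poor response or poor tolerability, so withdrawing such subjects can select on outcome even when the person deciding is blinded. Safety is the primary objective, and scheduled collection of new adverse events to Day 42 also stops for a subject withdrawn from the study.

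**Working it through.** **What happens to a violator withdrawn from the study**

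1. The subject is asked to attend one Early Termination visit, which includes EASI (Protocol 11.6.7). No later efficacy visit is described.
2. SAP 3.11 tabulates data under the visit recorded on the CRF. SAP 4.3.1 analyses only Baseline, Day 14, Day 28 and Day 42. No rule places an Early Termination EASI at any of these.
3. If withdrawal comes before Day 28, there is no Day 28 change, so the subject is absent from the ITT Day 28 t-test. Any Day 14 value already recorded stays in the Day 14 summary and t-test.
4. If withdrawal comes between Day 28 and Day 42, the Day 28 value stays in the Day 28 t-test.
5. SAP 4.3.1 fits the main model with PROC GLM and REPEATED, which uses only subjects with every repeated response. A subject withdrawn before Day 42 is left out of it entirely, including recorded Day 14 or Day 28 values.
6. The SAP's PP definition also requires a Day 28 visit (SAP 2.1 and 5). A subject withdrawn before Day 28 is therefore missing from both the ITT and the PP Day 28 comparisons, which moves the first toward the second.

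**The plan's own power figure**

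Inputs (Protocol 15.1, SAP 3.1): difference 3.9, SD 7.0, one-sided alpha 0.025, 52 per group, 130 randomized, 20% dropout.

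- Completers: 130 × 0.80 = 104, or 52 per group.
- Noncentrality at n = 52: 3.9 / (7.0 × √(2/52)) = 2.84 on 102 degrees of freedom. Exact t-test power is 80.3%, which agrees with the stated figure of more than 80%.

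**Power if removals come on top of the 20%**

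- Losing a further 10% of the 52 completers leaves 52 × 0.90 = 46.8, say 47 per arm. Noncentrality is 3.9 / (7.0 × √(2/47)) = 2.70 on 92 degrees of freedom, and power is 76.2%.
- Losing a further 10% of the 65 randomized per arm leaves 65 × 0.70 = 45.5, say 46 per arm, and power is 75.3%.
- If removals fall within the 20%, power stays at 80.3%.

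**Bias in the Day 28 difference**

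Let a share w of an arm be removed, with mean change worse by g EASI points than in those retained. The retained mean then differs from the full-arm mean by w × g. With the same g in both arms, the bias in the treatment difference is (difference in w) × g. The documents give neither quantity, so both are assumed.

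- Low: 0.05 × 3 = 0.15 points; 0.15 / 3.9 = 4% of the planned difference.
- High: 0.10 × 7 = 0.70 points; 0.70 / 3.9 = 18%.
- Equal removal and equal gap in both arms: zero.

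The bias favours B244 if more poor responders are removed from that arm, and works against it if more are removed from vehicle.

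**The case against.** The case on the other side has real substance.

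- **Who is affected.** A reader might infer that violators as a class drop out of the ITT results. The documents do not say so. The list is permissive, so only violators the sponsor chooses to withdraw are affected. They remain ITT members, and their earlier visits still count in the by-visit summaries and t-tests.
- **Withdrawal or stopping application.** The merged list may mean only that application stops for a violation. Protocol 7.3 describes withdrawal in terms of a participant refusing further visits, which a sponsor decision does not fit. The SAP disposition table has no sponsor or violation category, only a general one for other reasons. This stands as an ambiguity, and it is itself a reason to amend the text.
- **Adverse events.** A reader might infer that adverse event collection ends. It does not. Events are recorded at the Early Termination visit (Protocol 11.6.7), ongoing possibly related events are followed (7.5, 16.4), and later serious events judged related are reportable (16.7). What stops is scheduled collection of new events to Day 42.
- **Blinding.** Protocol 8.1 describes two liquids that differ in appearance, and a reader might infer that the sponsor could select by arm. Protocol 8.4 states that sponsor staff are blinded, the bottles are identical, and no route is described by which the sponsor would see a given subject's liquid. Blinding lowers the selection risk. It does not remove the part that arises because violations can follow response or tolerability.
- **Importance.** EASI is the secondary objective, and Protocol 15.4.5 labels efficacy p-values exploratory. That limits the weight of the point.

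**Conclusion.** The concern holds in a limited form. The plan lets the sponsor withdraw a violator from the study without stated criteria, under one reading of a merged list. When that happens, the subject's later data are lost from the ITT Day 28 t-test, and any subject withdrawn before Day 42 is lost from the repeated-measures model. The PP set already deals with major violations, so the analysis gains nothing from the study withdrawal.

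The size cannot be known from the documents. The bias of 0.15 to 0.70 EASI points (4% to 18% of 3.9) rests on an assumed 5 to 10 point difference in removal and an assumed gap of 3 to 7 points, where 7 is a full planned SD. A reader might infer that the trial is underpowered because of this clause. That does not follow, since the fall to 76.2% occurs only if removals exceed a 20% dropout allowance that is not restricted by cause. This is a worthwhile, inexpensive improvement and does not invalidate the design.

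**What to change.** In Protocol 7.3 and 13.4 and SAP 1.2.2:

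- separate withdrawal from the study from stopping application, and give reasons for each;
- remove protocol violation as a reason for study withdrawal;
- state that violations are recorded and handled through the PP set under SAP 2.2;
- state that the subject continues scheduled assessments and adverse event collection to Day 42 unless consent is withdrawn, and that those data are included in ITT.

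The decision on whether application continues stays with the existing rules, and no treatment rule is proposed here. All three places need the same wording, or the protocol and SAP will disagree. The separate provisions on interfering concomitant therapy (Protocol 7.3 and 13.4) and rescue medication (Protocol 8.14) are not changed by this.

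The cost is a wording amendment. Violators complete visits that are already scheduled, and ITT will include their post-violation data.

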7.4 Screen Failures

Data for screen and baseline failures, such as date and reason, will be collected in source documentation at the site

and will be transmitted to AOBiome.

7.5 Early Termination

Participants who have discontinued the study early will be evaluated by the Investigator at the Early Termination Visit. See the list of assessments to be performed at the Early Termination Visit in the Time and Events Table (Appendix A). Participants with ongoing AEs or SAEs believed to be possibly related to investigational product (IP) will continue to be followed until resolution or for 30 days as warranted by the nature of the AE.

8 STUDY TREATMENT

8.1 Investigational Product

Under normal conditions of handling and administration, IP is not expected to pose significant safety risks to site staff. A Material Safety Data Sheet describing the occupational hazards and recommended handling precautions will be provided to site staff if required by local laws or will otherwise be available from the Sponsor upon request.

Investigational product must be stored in a secure area under the appropriate physical conditions for the product. Access to and administration of the IP will be limited to the Investigator and authorized site staff. Investigational product must be dispensed or administered only to participants enrolled in the study and in accordance with the protocol.

The Investigator is responsible for study treatment accountability, reconciliation, and record maintenance. The Investigator or designated site personnel must maintain study treatment accountability records throughout the course of the study. The responsible person(s) will document the amount of study treatment received from and returned to the sponsor and the amount administered to participants. The required accountability unit for this study will be the bottle. Discrepancies are to be reconciled or resolved.

Product name:	B244, 30ml/bottle	Vehicle, 30ml/bottle
Dosage form:	B244 suspension	Vehicle solution
Unit dose strength:	4x10 ⁹ cfu/ml	50nM Na ₂ HPO ₄ -2mM MgCl ₂ (pH 7.6)
Route/administration/duration:	Topical application BID for 4 weeks	Topical application BID for 4 weeks
Dosing instruction:	Subjects will apply a total of 8 pumps of IP per application to all affected areas twice-aday (i.e. 8 pumps in the morning and 8 pumps again at night).	Subjects will apply a total of 8 pumps of IP per application to all affected areas twice-aday (i.e. 8 pumps in the morning and 8 pumps again at night).
	Applications should occur in the morning and at night for 4 weeks.	Applications should occur in the morning and at night for 4 weeks.
Physical description:	Odorless, cloudy, light pink suspension	Odorless, clear, and colorless suspension
Manufacturer/source of procurement:	AOBiome, LLC	AOBiome, LLC

The contents of the label will be in accordance with all applicable regulatory requirements. B244 and matching vehicle will be packaged in identical 30 ml white bottles.

8.2 Dose Changes

No dose changes are anticipated.

8.3 Storage conditions

All investigational drug supplies in the study will be stored in a secure, refrigerated (2-8°C) safe place, under the responsibility of the Investigator or other authorized individual.

8.4 Description of Blinding Method

This study will be double-blinded: neither Investigator(s), nor study participants, nor those involved in the conduct of the trial (including sponsor staff) will be aware of the treatment the participants are receiving.

8.5 Treatment Assignments:

This is a double blind study. Participants will be assigned to study treatment in accordance with the randomization schedule generated for the allocation of vehicle or B244 prior to the initiation of the trial. Randomization will be centrally-based and performed using an appropriate IWRS (an automated randomization system).

Each participant scheduled to receive investigational product (IP) will receive a randomization number at the time of randomization. The randomization number will be used to identify the study medication kit assigned to the participant and indicate the treatment to be administered to that participant.

8.6 Treatment Compliance

Study treatment must be dispensed or administered according to procedures described herein. Only participants enrolled in the study may receive study treatment. Only authorized site personnel may supply study treatment. Participants will record use of the study medication utilizing the study diary at the time of use each day. Participants will review study medication compliance with the Investigator or designee. Any missed doses, timing, and reason for missed dose will be recorded in the eCRF. There should be no doubling of doses to make up for missed doses. If a dose is missed, the next dose of study medication should be taken as scheduled.

Study staff will weigh the IP at the beginning of every visit. Weight will be recorded in the eCRF.

